6.3.3 Safety Assessments

The safety assessments will include AEs (Section 6.3.1), vital sign measurements, height and weight, concomitant medications, medical history, physical examination findings, transvaginal ultrasound, and clinical laboratory analyses (Section 6.6). Refer to Table 12–1 for a detailed schedule of the timing of study procedures.

6.3.3.1 Vital Sign Measurements

Vital sign measurements include oral temperature, seated blood pressure, pulse rate, and respiration rate. Vital sign measurements will be collected as indicated in Table 12–1.

6.3.3.2 Height and Weight

Height will be measured at baseline only and weight will be measured as indicated in Table 12–1.

6.3.3.3 Prior and Concomitant Medications

At the baseline visit, the investigator or designee must record the use of prescription and OTC medication taken within the prior 30 days. Concomitant medications (including prescription and OTC medications) will be assessed and recorded throughout the study (Table 12–1).

6.3.3.4 Transvaginal Ultrasound

Only for subjects with an intact uterus, transvaginal ultrasound will be performed at the baseline visit, Week 12 and every 24 weeks only (i.e., every other clinic visit) to observe changes in the endometrial stripe thickness (mm). Transvaginal ultrasound examinations will be evaluated locally.

6.4 Other Assessments

6.5 Pregnancy

This study will enroll only postmenopausal women who are not taking hormone products. In the unlikely event of a pregnancy, any pregnancy must be reported to pharmacovigilance within 2 weeks of learning of its occurrence, using the EDC system (Section 6.3.1.3). The pregnancy must be followed up to determine the outcome (including spontaneous miscarriage, elective termination, normal birth, or congenital abnormality) and status of mother and child, even if the subject was discontinued from the study. Pregnancy complications and elective terminations for medical reasons must be reported as an AE or SAE. Spontaneous miscarriages must be reported as an SAE.

Any SAE occurring in association with a pregnancy, brought to the investigator's attention after the subject has completed the study, and considered by the investigator as possibly related to the study treatment must be promptly reported to pharmacovigilance.

6.6 Laboratory Analyses

Any abnormal laboratory test results or other safety assessments, including those that worsen from baseline, felt to be clinically significant in the medical and scientific judgment of the investigator are to be recorded as AEs or SAEs.

However, any clinically significant safety assessments that are associated with the underlying disease, unless judged by the investigator to be more severe than expected for the subject's condition, are **not** to be reported as AEs or SAEs.

Laboratory analyses include the following:

- Complete blood count, including red blood cells, white blood cells, mean corpuscular volume, hemoglobin, hematocrit, platelets, and differential (basophils, eosinophils, lymphocytes, monocytes, and neutrophils)

- Comprehensive metabolic panel (Chem 16), including calcium, carbon dioxide, glucose, potassium, sodium, total protein, and kidney and liver function tests (serum ALT, AST, γ -glutamyl transpeptidase, and total and direct bilirubin) will be performed (the investigator may repeat these checks if clinically indicated)
- Fasting lipid panel, including total cholesterol, low-density lipoprotein, HDL, and triglycerides
- Hormone panel, including testosterone, free testosterone, and estradiol
- SHBG

7 Statistical and Analytical Plan

7.1 Primary Safety Endpoint

The primary objective in this study is to assess the safety and tolerability of GTx-024 3 mg administered once daily in relation to the following:

- Incidence of AEs
- Change from baseline in clinical laboratory evaluations
- Change from baseline in SHBG and testosterone levels
- Change from baseline in vital sign measurements
- Change from baseline in endometrial stripe thickness as assessed with transvaginal ultrasound (only in subjects with an intact uterus)

7.2 Secondary Efficacy Endpoints

The secondary objective in this study is to assess the efficacy of GTx-024 3 mg administered once daily at each scheduled visit in relation to the following:

- Change from baseline in the mean number of stress incontinence episodes per day as measured with the 3-day voiding diary
- Change from baseline in subject-reported impression of SUI severity as measured with the PGI-S
- Improvement relative to baseline in subject-reported impression of SUI improvement as measured with the PGI-I
- Change from baseline in the mean number of urge incontinence episodes per day as measured with the 3-day voiding diary
- Change from baseline in the mean number of total incontinence episodes (stress + urge) as measured with the 3-day voiding diary

These analyses will be described in further detail in the statistical analysis plan (SAP).

7.3 Sample Size Calculation

No power calculations were carried out, as no formal statistical analysis will be performed.

7.4 Analysis Sets

Data analysis will be performed on a safety analysis set (SAS) and a full analysis set (FAS).

The SAS set contains all subjects in the study who receive ≥ 1 dose of study drug. All safety analyses will use the SAS.

The FAS is used for efficacy analysis. The FAS consists of all randomized subjects who receive ≥ 1 dose of study drug and have ≥ 1 postbaseline primary efficacy assessment (3-day voiding diary). Further details will be provided in the SAP.

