Safety Assessments:	
Safety assessments will include the following:
 
 • AEs • Clinical laboratory analyses • Levels of sex hormone–binding globulin and testosterone • Endometrial stripe thickness as assessed with transvaginal ultrasound (only for subjects with an intact uterus) 
Other standard safety assessments will include vital signs, height and weight measurements, concomitant medications, medical history, and brief physical examination findings.

Efficacy Assessments:	
The following assessments will be conducted to evaluate efficacy:
 
 • 3-Day Voiding Diary 
The 3-day voiding diary is a study tool for subjects to report each episode of urinary void. The subject will be asked to record each episode of urinary leakage, the type (stress or urge) of leakage, and the severity of leakage. Subjects will also be asked to record each episode of voluntary urinary void and fluid intake.
 
 • PGI-S 
The PGI-S is a global rating of subject-reported impression of severity using a 4-point scale. Validity of the PGI-S has been established for application in SUI.
 
 • PGI-I 
The PGI-I is a global rating of subject-reported impression of improvement using a 7-point scale. Validity of the PGI-I has been established for application in SUI.

Study Drug:	Study drug will be provided as softgel capsules in bottle packaging. All subjects will receive GTx-024 3 mg once daily.
Sample Size Calculation:	No power calculations were carried out, as no formal statistical analysis will be performed.
Analysis Sets:	The safety analysis set (SAS) contains all subjects in the study who receive ≥ 1 dose of study drug. All safety

	
analyses will use the SAS.
 
The full analysis set (FAS) contains all randomized subjects who receive ≥ 1 dose of study drug and have ≥ 1 postbaseline primary efficacy assessment (3-day voiding diary). All efficacy analyses will use the FAS.

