6.1.2 Study Visits 1 to 3: Weeks 4 to 12, Clinic Visit

The subject will return to the study site for a clinic visit as per the schedule of events described in Table 12–1. Concomitant medications and AEs will be reviewed. Weight and vital signs will be measured.

The 3-day voiding diary provided to the subject at her previous visit will be collected and completion verified. The subject will be provided with a new 3-day voiding diary and instructed to complete it within the week preceding her next study visit. The subject will also complete the PGI-S and PGI-I during each site visit. Blood will be drawn for a CMP, CBC, lipid panel, hormone panel, and SHBG tests.

Study drug will be dispensed with administration instructions. The medication identification number assigned to the subject will be noted in the eCRF for study drug accountability. The subject will be reminded to bring all unused study drug (in its original packaging) to her next clinic visit.

A transvaginal ultrasound examination will be performed in subjects with an intact uterus only at Visit 3.

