6.2.1 Three-Day Voiding Diary

Subjects will record all urinary voids, specifying each episode of urinary leakage, including type (stress or urge). Fluid intake will also be recorded as well as any episode of vaginal discharge or spotting.

In each 3-day voiding diary, subjects are to record voiding data for 3 consecutive days in a paper diary. To be considered valid, each 3-day voiding diary must be recorded within 7 days on either side of a planned visit.

Three-day voiding diaries are reliable measures of the mean number of urinary incontinence episodes per day, incontinence type, mean number of voids per 24 hours, and mean number of voids during sleeping hours.

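### The only efficacy set requires at least one post-baseline voiding diary, so treated women with PGI-S or PGI-I data but no diary at any visit drop out of every PGI summary

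*Combined protocol and SAP*

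**What the plan says.** Section 7.4 sets up two analysis sets. The safety set is everyone who takes a dose. For the other, "The FAS is used for efficacy analysis", and membership requires at least one dose and at least one "postbaseline primary efficacy assessment (3-day voiding diary"). The synopsis, under Analysis Sets, leaves no exception: "All efficacy analyses will use the FAS". No other efficacy set is defined.

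Section 7.2 lists five secondary efficacy endpoints. Three come from the diary. The other two do not: "Change from baseline in subject-reported impression of SUI severity as measured with the PGI-S" and "Improvement relative to baseline in subject-reported impression of SUI improvement as measured with the PGI-I".

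The two kinds of data are collected differently. For Visits 1 to 3, section 6.1.2 says "The subject will also complete the PGI-S and PGI-I during each site visit". Section 6.1.4 has both scales completed at the end-of-study visit, and Table 12-1 schedules them at the long-term visits too. For the diary, "subjects are to record voiding data for 3 consecutive days in a paper diary" (section 6.2.1), and the woman is "instructed to complete it within the week preceding her next study visit" (section 6.1.2).

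Two further statements bear on the point. Section 7.6 rules out imputation. Section 4.2.2 commits to using the data of all subjects in reporting and analysis, and names early withdrawals and early discontinuations expressly.

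**The concern.** The FAS makes one instrument the condition for analysing another. A woman can attend, complete both scales at the site, and have no diary because she did not fill it in at home or did not bring it. If that is so at every post-baseline visit she makes, she is outside the FAS and her PGI responses enter no efficacy summary, although they were collected and are complete.

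The women affected are not a random sample of those treated. They have few post-baseline visits or repeatedly do not keep the diary. Section 4.2.2 promises that early withdrawals will be used, so the two sections cannot both be followed for these women. The PGI summaries, possibly with 95% confidence intervals (section 7.6), are all that the study reports on these scales, and nothing in the protocol explains why a diary should be a condition for them.

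**Working it through.** **Step 1. Check the rule against the endpoints.** The protocol gives no figure to reproduce: it has no power calculation (section 7.3) and no diary-completion rate.

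| Item | Source | Needs a diary? |
|---|---|---|
| Entry to the FAS | 7.4, synopsis | Yes, at least one at any post-baseline visit |
| Stress, urge and total episodes | 7.2 | Yes |
| PGI-S change | 7.2, 6.1.2, 6.1.4, Table 12-1 | No |
| PGI-I | 7.2, 6.1.2, 6.1.4, Table 12-1 | No |
| Use of all subjects' data | 4.2.2 | No condition stated |

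A treated woman with PGI data and no post-baseline diary meets the data needs of the two PGI endpoints and fails the entry rule. The omission follows from the text.

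**Step 2. Who is affected.** Assume that a diary is missing at each attended visit with probability *q*, independently across visits. The chance of no diary after *k* post-baseline visits is *q*^*k*. The range *q* = 5% to 30% is an assumption.

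| Visits *k* | *q* = 5% | *q* = 30% |
|---|---|---|
| 1 | 5% | 30% |
| 2 | 0.05² = 0.25% | 0.30² = 9% |
| 3 | 0.05³ = 0.0125% | 0.30³ = 2.7% |

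The loss shrinks quickly as visits accumulate. It sits with women who have one or two post-baseline visits and, where misses cluster within a woman instead of being independent, with persistent non-completers.

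**Step 3. Possible effect on a PGI-I proportion.** Let *m* be the share of treated women with post-baseline PGI-I data who have no diary. Let *p* be the responder proportion in the FAS and *p* − *d* the proportion among the women left out. The protocol defines no PGI-I responder, so take any fixed grouping of the seven categories. Among all women with data the proportion is

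(1 − *m*)*p* + *m*(*p* − *d*) = *p* − *md*,

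so the FAS figure is too high by *m* × *d*. Both inputs are assumed. Results in percentage points:

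| *m* | *d* = 20 | *d* = 40 | *d* = 60 |
|---|---|---|---|
| 1% | 0.2 | 0.4 | 0.6 |
| 2% | 0.4 | 0.8 | 1.2 |
| 5% | 1.0 | 2.0 | 3.0 |
| 10% | 2.0 | 4.0 | 6.0 |

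If the women left out did as well as the rest, *d* = 0 and there is no shift. If they did better, its sign reverses.

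**Step 4. Why shares and not head counts.** The figure of 500 in section 4.1 is an upper limit. Under section 4.1.1 the eligible pool is subjects 226 to 493, which is 493 − 226 + 1 = 268 women, plus only the placebo women among the first 225. Even counting all 225 gives 268 + 225 = 493. The true pool is smaller by an amount that the documents do not state.

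**The case against.** The strongest reply is that the loss is narrow and of little consequence. One diary at any post-baseline visit brings in all of a woman's PGI data from every visit. Sites verify diary completion at visits, and women who stop early are asked back for end-of-study assessments, which include a diary as well as the PGI scales. The study is open-label, single-treatment and descriptive, so no test is affected, and the primary safety analysis uses everyone dosed. A single common set keeps the population the same across endpoints. Section 7.4 also defers detail to a separate SAP, which is not in the text available and might define endpoint-specific sets. The values left out of the summaries would still appear in the data listings.

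Most of this stands as a limit on size. It does not remove the point. The synopsis already commits all efficacy analyses to this set, so the rule is stated and not merely left open. The conflict with section 4.2.2 remains, and a common population is a weak reason to omit completed responses from a descriptive summary.

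Several stronger readings are tempting and are not supported:

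- A reader might infer that PGI data are lost at each visit without a diary. The condition is one diary at any visit.
- A reader might infer that a diary outside the 7-day window of section 6.2.1 blocks entry. Section 7.4 does not refer to that window, and nothing says that it governs the FAS.
- A reader might infer that the reference to randomized subjects shrinks the set. All of these women were randomized in G201002, so the word excludes nobody.

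**Conclusion.** The point holds in limited form. As written, a treated woman with post-baseline PGI data and no post-baseline diary at any visit is omitted from every PGI summary, contrary to section 4.2.2. That part rests on the text alone.

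The size is not known and is probably small. With 1% to 10% left out and a responder rate 20 to 60 points lower among them, the reported PGI-I proportion would be 0.2 to 6 points too high; neither range comes from the documents. A reader might conclude that the rule makes the drug look better than it is. Such a bias is plausible, because women who leave early or do not keep the diary may have done less well, but nothing in the documents shows it. Safety results are unaffected. The change is worth making because it restores data already collected at almost no cost.

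**What to change.** In section 7.4 and in the synopsis, define the efficacy set as all subjects who receive at least one dose. State that each endpoint is analysed in those with at least one post-baseline value of that endpoint and, for endpoints expressed as change, a baseline value. PGI-I is first collected at Visit 1 and is itself a comparison with the time before treatment, so it needs no baseline value. A diary is then required only for the diary endpoints, and the rule agrees with section 4.2.2. The separate SAP should carry the same definition.

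As wording only, replace the description of the diary as a primary efficacy assessment, since the primary endpoint is safety and all efficacy endpoints are secondary.

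The cost is one changed definition in two places and no new data. The downside is that n will differ slightly between endpoints, so each table should show its own n.

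The change does not address the separate selection that arises when by-visit summaries cover only the women still in the study.

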7.5 Description of Subgroups to be Analyzed

No subgroup analyses are planned.

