Methods of Analysis:	
A separate statistical analysis plan (SAP) will be finalized, providing detailed methods for all endpoints. In general, descriptive or summary statistics (n, mean, standard deviation, median, minimum and maximum values for continuous variables, and number [%] of subjects in each category for categorical variable) will be provided by visit. Source data for summary tables and statistical analyses will be presented as subject data listings. No imputation for missing values will be done.
 
All statistical analyses will be performed using SAS (version 9.3 or higher). No formal statistical analysis will be performed as the open-label extension study is not powered for inferential statistics. Two-sided 95% confidence intervals will be provided where appropriate.
 
Change from baseline will be between baseline (Day 0) and scheduled visits. The SAP will specify up to which visit summaries will be produced, as not all subjects will have been in the study for the same length of time. Further details on the analysis of the efficacy endpoints will be provided in the SAP.

Safety Analyses

All safety parameters (including AEs) will be summarized using the SAS.

All AEs will be coded using the latest version of the Medical Dictionary for Regulatory Activities. All treatment-emergent AEs will be summarized and presented in the listings according to the number of subjects who report an event, the percentage of subjects with that event, the number of events, and the grade, duration, and relationship to treatment. Percentages will be based on the number of subjects who received treatment during the open-label extension study.

Efficacy Analyses

The primary analysis will be conducted on the primary endpoints at scheduled visits using the FAS.

For continuous and ordinal endpoints, the treatment effect will be summarized descriptively by visit.

List of Abbreviations

Abbreviation	Definition
AE	adverse event
ALT	alanine aminotransferase
AST	aspartate aminotransferase
CBC	complete blood count
CFR	Code of Federal Regulations
CMP	comprehensive metabolic panel
EDC	electronic data capture
eCRF	electronic case report form
FAS	full analysis set
FDA	US Food and Drug Administration
GCP	Good Clinical Practice
HDL	high-density lipoprotein
ICF	informed consent form
ICH	International Council for Harmonisation
INR	international normalized ratio
IRB	institutional review board
MedDRA	Medical Dictionary for Regulatory Activities

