3.1 Study Design

This is a multicenter, Phase 2, open-label extension study that will assess the long-term safety and tolerability of GTx-024.

The current study will enroll the following subjects from G201002:

- From the first 225 subjects enrolled in G201002, only subjects randomly assigned to the placebo group and who have completed the 12-week treatment period and 16-week durability period will be allowed to enroll in this study, once data from G201002 are unblinded. Placebo subjects who enrolled in the durability extension study (G201003) will be allowed to discontinue participation in G201003, once data from G201002 have been unblinded
- From Subject 226 onwards, any subject who was randomly assigned to any treatment group and who has completed the 12-week treatment period and the 4-week follow-up period in Study G201002

All subjects in this study will receive GTx-024 3 mg orally, once daily.

The study consists of the following visits:

Baseline (Day 0)

Subjects will be evaluated, and an additional written informed consent for the open-label extension study will be obtained. Procedures will be performed at baseline as specified in the schedule of events (Table 12–1) for the study.

Long-term Open-label Extension Period

Subjects who continue to meet the eligibility criteria will attend clinic visits at 4-week intervals for the first 12 weeks of the open-label extension study (i.e., Weeks, 4, 8, and 12). Following the first 12 weeks, subjects will attend clinic visits every 12 weeks (i.e., 12 weeks from Visit 3 onwards). At each clinic visit, study procedures will be performed as specified in the schedule of events (Table 12–1).

There is currently no planned end to this study; instead, subjects will be on treatment and followed until marketing approval is granted to GTx-024 or until the withdrawal of the Investigational New Drug application. If marketing approval is granted to GTx-024, a plan

for the transition of subjects from study drug to commercial drug product or other therapy will be implemented.

Data from this open-label extension study will be used to assess the long-term safety and tolerability of GTx-024.

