4.1.1 Inclusion Criteria

Each subject must meet all of the following criteria to be enrolled in this study:

1. Be an eligible subject from G201002, where an eligible subject is defined as:
 - a. one of the first 225 subjects who were randomly assigned to the placebo group in G201002 and who have completed the required treatment and durability periods of that study, or;
 - b. any subject from 226 onwards, who was randomly assigned to any treatment group and who completed the required treatment and follow-up periods of that study
2. Be able to read, understand, and provide written, dated informed consent prior to enrollment in the current study and be likely to comply with the study protocol and communicate with study personnel about AEs and other clinically important information
3. Provide written consent to participate in the study within the following timeframes:
 - a. for G201002 Subjects 1-225, within 30 days after the unblinding of G201002 (subjects who consent to participate in G201003 will be allowed to discontinue from that study and consent to this study upon unblinding of G201002)
 - b. for G201002 Subjects 226-493, within 30 days of completing both the treatment and follow-up period of G201002

4. Agree to maintain a stable dose of any medication known to affect lower urinary tract function, including but not limited to anticholinergics, tricyclic antidepressants, beta-3 adrenergic agonists, or α -adrenergic blockers, throughout the duration of the study

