6.1.1 Baseline (Day 0)

The study will be explained in detail, and adequate time will be allowed for answering questions from a potential subject before she signs the institutional review board (IRB)–approved informed consent document. Informed consent will be obtained from those potential subjects who meet initial inclusion/exclusion criteria and express willingness to participate before study site personnel conduct any study assessments of such subjects.

Once informed consent is obtained, the subjects will be assigned a subject number and a detailed interview will be conducted with the subject about her concomitant medications, and recent medical history will be evaluated. Height and weight will be measured, and vital signs will be assessed as presented in Table 12–1.

The subject’s eligibility criteria will be reviewed. During the visit, the subject will complete the PGI-S. Blood will be drawn for a comprehensive metabolic panel (CMP), complete blood count (CBC), lipid panel, hormone panel, and SHBG tests. A baseline transvaginal ultrasound examination will also be performed in subjects with an intact uterus.

The subject will be provided with a 3-day voiding diary and instructed to complete the 3-day voiding diary within the week preceding her next study visit.

Study drug will be dispensed with administration instructions. The medication identification number assigned to the subject will be noted in the eCRF for study drug accountability. The subject will take the first dose of study drug during the baseline visit. The subject will be reminded to bring all unused study drug (in its original packaging) to her next clinic visit. Any subject who prematurely discontinues the study or study drug will be asked to return to the study site and complete end-of-study assessments.

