7.6 Statistical Analysis Methodology

A separate SAP will be finalized, providing detailed methods for all endpoints. In general, descriptive or summary statistics (n, mean, standard deviation, median, minimum and maximum values for continuous variables, and number [%] of subjects in each category for categorical variable) will be provided by visit. Source data for summary tables and statistical analyses will be presented as subject data listings.

All statistical analyses will be performed using SAS (version 9.3 or higher). No formal statistical analysis will be performed, as the open-label extension study is not powered for inferential statistics. Two-sided 95% confidence intervals will be provided where appropriate. No imputation will be done for missing data. The SAP will specify up to which visit summaries will be produced, as not all subjects will have been in the study for the same length of time. Further details on the analysis of efficacy endpoints will be provided in the SAP.

The study period is defined as baseline (Day 0) through end of study. Change from baseline will be between baseline (Day 0) and scheduled visits.

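### No section commits to showing results by prior G201002 treatment, although the extension pools first exposure to GTx-024 with re-exposure from a common Day 0

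*Combined protocol and SAP*

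**What the plan says.** **Entry.** Sections 3.1 and 4.1.1 give two routes into one arm. G201002 Subjects 1-225 may enter only if they had placebo. The second route is wider: "From Subject 226 onwards, any subject who was randomly assigned to any treatment group" may enter after completing 12 weeks of treatment and 4 weeks of follow-up. Everyone then receives GTx-024 3 mg once daily (Sections 3.1 and 5.6).

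**Timing.** For the later group, the consent limit in Section 4.1.1 reads "for G201002 Subjects 226-493, within 30 days of completing both the treatment and follow-up period of G201002". Under the Day 0 heading of Section 3.1, "an additional written informed consent for the open-label extension study will be obtained". Section 6.1.1 adds: "The subject will take the first dose of study drug during the baseline visit".

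**Analysis.** Section 7.4 has one safety set and one full analysis set: "The SAS set contains all subjects in the study who receive" at least one dose. Section 7.6 fixes the reference point: "Change from baseline will be between baseline (Day 0) and scheduled visits". The safety part of the synopsis methods uses one denominator for adverse events: "Percentages will be based on the number of subjects who received treatment during the open-label extension study". Section 7.5, in full, is "No subgroup analyses are planned". Section 7.6 also plans subject listings and leaves detailed methods to a separate SAP, which is not part of the document available here.

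**The concern.** The primary objective is long-term safety, so length of exposure is the natural axis for reading the tables. At the same extension visit, a prior-placebo subject and a prior-GTx-024 subject have been on drug for different lengths of time. The re-exposed group is also selected: its members had already completed 12 weeks of G201002 treatment.

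The protocol itself describes effects that depend on time. Section 3.1.1.1 reports ALT increases recorded as adverse events in 20.8% of subjects at 3 mg against 0% on placebo, mostly resolving with continued dosing. It times the recovery of HDL from the start of treatment, at about 12 months. For a re-exposed subject, treatment started in G201002 and not at extension Day 0. A pooled mean or percentage cannot show whether a finding belongs to first or to longer exposure.

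For change scores, Day 0 precedes any GTx-024 for prior-placebo subjects. For prior-GTx-024 subjects it follows a recent course of treatment. The PGI-I form (Appendix 12.3) asks for a comparison with the state before medication in this study, which on its natural reading is the state at re-entry.

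**Working it through.** The plan has no power calculation and no figure on this point to reproduce. The check is of scale only.

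**Inputs from the protocol.** Later cohort: Subjects 226-493, so 493 - 226 + 1 = 268. Earlier cohort: 225, placebo only. G201002 treatment: 12 weeks. Follow-up: 4 weeks. Consent limit: 30 days.

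**Assumed, because not given.** The placebo share s in G201002 (1/2, 1/3 or 1/4, that is 1:1, 1:1:1 or 1:1:1:1). The fraction f of earlier placebo subjects who enter. The fraction g of the later cohort who enter, equal across arms.

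**Off-drug gap at Day 0, prior GTx-024.** 4 + (0 to 30/7) = 4.0 to 8.3 weeks, if consent falls within the limit and dosing takes place at that visit.

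**Share of prior-GTx-024 subjects.** p = 268·g·(1 - s) / (225·s·f + 268·g)

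| Roll-over | s = 1/2 | s = 1/3 | s = 1/4 |
|---|---|---|---|
| Full (f = 1, g = 1) | 134/380.5 = 35% | 178.7/343 = 52% | 201/324.25 = 62% |
| No one from Subjects 1-225 (f = 0, g = 1) | 134/268 = 50% | 178.7/268 = 67% | 201/268 = 75% |
| Half of Subjects 226-493 (f = 1, g = 0.5) | 67/246.5 = 27% | 89.3/209 = 43% | 100.5/190.25 = 53% |

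These are scenarios, not bounds. More uneven roll-over would widen the range.

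**Weeks on drug at extension week w, full compliance.** Prior placebo: w. Prior GTx-024: w + 12.

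| Visit | Prior placebo | Prior GTx-024 | Ratio |
|---|---|---|---|
| Week 4 | 4 | 16 | 4.0 |
| Week 12 | 12 | 24 | 2.0 |
| Week 24 | 24 | 36 | 1.5 |
| Week 48 | 48 | 60 | 1.25 |

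**What a pooled Week 12 column describes.** Mean weeks on drug = 12 + 12p. Under full roll-over and before dropout this is 16.2, 18.3 or 19.4 weeks.

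These are weeks, not dose. The protocol does not give the G201002 doses, so 12 prior weeks need not equal 12 weeks at 3 mg.

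**The case against.** The strongest reply is that Section 7.5 speaks of subgroup analyses and not of table columns. A descriptive column by prior treatment is not clearly a subgroup analysis, layout may be settled in the SAP, and listings are planned. A reader might infer that Section 7.5 rules out any such display, or that the data could not be split. The documents support neither: the SAP could add the display, and the prior arm is known once G201002 is unblinded. What remains is that nothing in the protocol commits to it. The stated deferrals to the SAP concern endpoint methods, analysis-set and efficacy detail, and the last visit to be summarized.

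Section 7.6.1 bases percentages on the number receiving each treatment, Section 5.1 mentions a randomization code, and Section 7.4 refers to randomized subjects. These could hint that the parent arm is carried forward. But only one treatment is given, and none of the three names prior treatment as a column or stratum.

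A reader might also infer that pooling biases the safety rates, or that change from Day 0 understates efficacy. The documents do not show this. They give no residual effect at re-entry and do not say how an off-drug gap alters the course of ALT or HDL. If the two groups behave alike, pooling hides nothing. No test or decision rule is affected, and the relative exposure gap shrinks at later visits. All of this stands and limits the weight of the point. Lack of power is no defence, however, because a descriptive column needs none.

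On the PGI-I, Section 7.2 defines improvement relative to baseline, so a Day 0 reference is by design. How subjects would read the form is an inference.

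**Conclusion.** The point holds in a limited form. The pooled summaries are valid for the mixed cohort. Followed as written, however, the plan does not let long-term safety results be read by length of exposure. It also takes change for prior-GTx-024 subjects from a point that is not an untreated baseline if any effect remains.

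The mixture is substantial in every scenario tried, from 27% to 75% prior GTx-024, so neither group can be ignored. Those shares rest on assumed allocation and roll-over. The 12-week difference rests on full compliance and counts weeks only. It is firm that entry is mixed, that Day 0 is the common baseline and that no subgroup analysis is planned. It is less certain that the final tables would have a single column, because the SAP was not available. This is a cheap improvement to the plan, not an error that invalidates it.

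**What to change.** Amend Section 7.5 to say:

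- No inferential subgroup analyses are planned.
- Safety and efficacy summaries will be shown descriptively by prior G201002 treatment (placebo; GTx-024) as well as in total. The SAP will state whether G201002 dose groups are combined.
- Where G201002 collected the measure, change from the G201002 pre-treatment baseline will be shown for both groups as a supplement to change from Day 0.

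Giving the supplement for both groups matters: prior-placebo subjects may also have changed during G201002, and the columns should share a reference point. The PGI-I cannot be re-anchored, so show it by prior treatment only.

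The cost is protocol and SAP wording, a merge of G201002 arm and baseline data, and smaller numbers per column. Under full roll-over the columns would hold about 246 prior-placebo and 134 prior-GTx-024 subjects at 1:1, 164 and 179 at 1:1:1, or 123 and 201 at 1:1:1:1 (493·s and 268·(1 - s)). No visits, assessments or tests are added.
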